Fragility Fracture	A fracture that occurred with minimal trauma at a typical site of osteoporotic fracture that would be unlikely to cause fracture in a non-osteoporotic adult.
Postmenopause	No menses for at least one year, OR 6 months of spontaneous amenorrhea with serum FSH levels >40 mIU/mL, OR at least 6 months after a surgical bilateral oophorectomy with or without hysterectomy.
Asthma	A disease characterized by recurrent attacks of breathlessness and wheezing, varying in severity and frequency from person to person, with spirometry showing the FEV1 improves $> 12\%$ following administration of a bronchodilator.
Chronic Obstructive Pulmonary Disease	A lung disease characterized by chronic obstruction of lung airflow that interferes with normal breathing and is not fully reversible, as confirmed in spirometry by a 75-80% of the FVC comes out in the first second and a FEV1/FVC ratio $< 70\%$ with symptoms of the disease.
Diabetes Mellitus	A disease characterized by recurrent or persistent hyperglycemia, and is demonstrating any one of the following: 1. Fasting plasma glucose level ≥ 7.0 mmol/l (126 mg/dl); 2. Plasma glucose ≥ 11.1 mmol/l (200 mg/dl) 2 hours after a 75-g oral glucose load as in a glucose tolerance test; 3. Symptoms of hyperglycemia and casual plasma glucose ≥ 11.1 mmol/l (200 mg/dl); 4. Glycated hemoglobin (HbA1C) ≥ 48 mmol/mol (≥ 6.5 DCCT %).
Confounding	A confounding variable or a confounder is a variable other than the risk factor and outcome under study that is independently related both to the risk factor and to the outcome. A confounder can create an apparent association between the risk factor and outcome or mask a real one

PROTOCOL SUMMARY

Title	An Observational, Cross-Sectional Study Investigating the Prevalence of Vertebral Fractures among Community-Dwelling Postmenopausal Women in China (The Chinese Vertebral Osteoporosis Study, ChiVOS)
Vendor/Collaborator	Not applicable
Rationale	Osteoporosis leads to major fractures including vertebral fractures. Vertebral fractures are a strong predictor of any fracture risk and thus impact the screening of osteoporotic patients and pharmacological treatments. Epidemiological studies investigating the prevalence of vertebral fractures have been increasing in recent years; however, in China, has so far been few.
Primary Objective(s)	To investigate the prevalence of radiographic vertebral fractures in community-dwelling postmenopausal women in China
Study Design	Observational, population-based, cross-sectional design with a clustered simple randomization sampling
Study Population	Community-dwelling postmenopausal women aged 50 or over
Study Duration	A 6-9 month of enrollment period
Exposure and Outcome	VF as confirmed by radiology imaging; osteoporosis as suggested by DXA T-score or a proven fragility fracture
Statistical Methods	Prevalence rate by point estimate and 95% CI with model-based statistical analyses for VF risk factors
Sample Size and Power Calculations	A sample size of 2700 women in 5 regions in China. Sample size calculation based on age-specific VF prevalence.
Limitations	Incident VF cannot be assessed in a cross-sectional study; biases for interview-based questionnaire.

1 Background and Rationale

1.1 Background

Osteoporosis is a multi-factorial skeletal disease characterized by low bone mass and a structural deterioration of the macro and microarchitecture of bone tissue, leading to increased bone fragility and susceptibility to fracture [1]. Osteoporosis is considered a global public health concern, due to its prevalence worldwide. Yet its pathogenesis has not been clear. Osteoporosis affects numerous people, of both sexes and all races, and its prevalence increases as the population ages. Currently, it has been estimated that over 200 million people, including 75 million in the United States, Western Europe and Japan [2], have osteoporosis. Approximately 30% postmenopausal women are osteoporotic in the US and in Europe [2]. In China, an observational study has suggested a total of 54 million women aged 50 or above have osteoporosis, representing a prevalence of 27.3% in this affected population [3].

Osteoporosis is often called a 'silent disease'. Its diagnosis relies on a bone mineral density (BMD) value by dual-energy X-ray absorptiometry (DXA, DEXA) [1] and/or a proven fragility fracture at major skeletal sites [2, 3]. It has a significant clinical impact because of the association with an increased risk of fractures at major skeletal sites including the hip, the vertebrae, and the distal forearm. At least 40% of osteoporotic women [4] and 15-30% of men [5] experience one or more fragility fractures in their remaining lifetime. The combined lifetime risk of hip, forearm and vertebral fractures (VF) is 40%, being equivalent to the risk of cardiovascular diseases [6]. Moreover, an initial osteoporotic fracture by any type is a major risk factor for a new fracture [7, 8]. For instance, patients with a history of VF have a 2.3-fold increased risk of a future hip fracture and a 1.4-fold increase in risk of distal forearm fracture [8]. These fragility fractures lead to a substantial loss of quality of life [6, 9], an increased hospitalization [10, 11] and an excessive risk of mortality [12], and thus cause a tremendous socioeconomic burden. Currently, Chinese therapeutic guideline has recommended a routine screening program, consisting of blood chemistry, chest-waist spine radiology, and DXA, for the diagnosis and treatment of osteoporosis in various populations including postmenopausal women with or without other socioeconomic and/or clinical risks.

Vertebral fractures are the most common manifestation of osteoporosis [13]. The deformities of the vertebral bodies, identified with imaging of the lateral spine, are usually asymptomatic and may initially be felt or presented in the form of severe back pain, loss of height or spinal deformities such as kyphosis. Prevalent radiographic vertebral fractures, most commonly in the thoracolumbar transition zone or midthoracic region, can cause reduced mobility and disability [14-16], and thus reduced health-related quality of life [15] and a higher risk of death in the elderly [17]. Vertebral fractures are prevalent, which increases with age. In the US, the incidence of vertebral fractures accounts for 700,000 of the 1.5 million osteoporotic fractures annually [18]; in Europe, the overall prevalence of radiographic vertebral fracture is estimated at approximately 12% in osteoporotic women [10]. The prevalence among Caucasian women is as high as 30% in the population aged 80 years or older [19]. Unlike other types of fractures, for

example, hip fractures, which are less in Asians, vertebral fractures have been reported to be as frequent in Asian women [20]. Based on separate local cross-sectional studies conducted in Beijing, shanghai and Chengdu, a total of 1.8 million people were estimated to have a vertebral fracture annually in China [3]; the prevalence is 15% in women who are 50 years of age or elder, and is between 36% and 39% in those who are 80 years of age or elder, respectively [3].

In the clinical setting, lateral thoracic and lumbar spinal radiographs are the standard procedure for the diagnosis and assessment of vertebral fractures. Several qualitative and quantitative approaches have been developed to adjudicate a vertebral fracture, including a widely accepted Genant's semi-quantitative technique [21, 22]. However, in contrast to other fractures, most vertebral fractures receive little clinical attention and remain undiagnosed at the time of occurrence or during the lifetime [6, 9, 13]. The reason may be that most (up to 75%) vertebral fractures are absent from clinical signs and symptoms [22], and even only one fourth to one third of incident radiographically identified vertebral fractures are clinically diagnosed [23, 24]. As indicated in a previous report in 2011, there were an estimated 9 million new osteoporotic fractures worldwide in a particular year, among which only 1.4 million were clinical vertebral fractures and thus were medically cared [25]. Nevertheless, vertebral fractures are proven a strong predictor of a future fracture risk, at any skeletal site, which is independent of BMD [13, 26]. Women who have 2 or more vertebral fractures may have a 7-fold risk in having another vertebral fracture within one year, a 2 to 3-fold risk in having a future non-vertebral fracture, and a 2-fold risk in having a hip fracture, respectively [27]. Based on therapeutic guidelines [1, 2], a vertebral fracture is consistent with a diagnosis of osteoporosis (BMD DXA T-score ≤ 2.5) [1, 2] in the absence of a bone density diagnosis by dual-energy X-ray absorptiometry (DXA, DEXA). An early diagnosis of vertebral fractures is indicated for subsequent pharmacological therapy for osteoporosis, which is critical to prevent an add-on osteoporotic fracture.

1.2 Rationale

Historically, population-based studies of vertebral fracture have been few. This may be due in part to the variable clinical presentation of vertebral deformity, as well as to variation in opinion as to the extent of deformity which constitutes a significant vertebral fracture. The development of morphometric and semi-quantitative visual techniques has enabled a number of studies to explore both the prevalence and incidence of vertebral fractures in the US [28] and Canada (CaMOS [29]), typical European communities (EPOS [30], EVOS [31], FRAVO [32]) and Japan [33], and in developing countries including Latin American countries [34], India [35], and China [36]. These studies have elucidated a global prevalence of vertebral fractures and provided a possible comparison of epidemiological data among different populations with varied geographic locations, environment and culture, and lifestyle. In contrast with hip fractures, the prevalence and incidence of vertebral deformities appears relatively homogeneous across different regions of the world. The prevalence tends to increase with age among men and women.

Product: MK-0217A
Protocol/Amendment No.: 911

On the other hand, variations in sample size (CaMOS n=6433, EVOS n=17,342 FRAVO n=842; LAVOS n=1922, DeVOS n=808, Beijing Osteoporosis Project n=402), sampling methodology (age-stratified population-based sampling vs. simple survey sampling), and assessment criteria are seen across the studies. The extent to which these variations represent study bias remains uncertain. Notably, a fine comparison of VF epidemiology between Western societies and China is difficult. Among few population-based studies conducted in China, the Beijing Osteoporosis Project was the first well-documented epidemiology study. The study group performed a randomized sampling and previously validated assessment from the US [36]. However, this study was in a relatively small scale and only represented a local population from the city of Beijing. Another study was the Hong Kong Osteoporosis Study, in which 2178 postmenopausal women have been enrolled [37]. Considering geographic location, lifestyle, and clinical practice, study results may not be generalized to the entire Chinese population. Other cross-sectional studies investigating osteoporosis and fractures neither aimed at a primary collection of VF epidemiology data [39], nor designed adequately to minimize study bias [40]. Therefore, a well-designed, nationwide, population-based epidemiological investigation of the prevalence of vertebral fractures and related risk factors in China is necessary.

2 Objectives and Hypotheses

2.1 Primary Objective(s) & Hypothesis(es)

To investigate the prevalence of vertebral fractures in community-dwelling postmenopausal women in China

2.2 Secondary Objective(s)

1. To investigate the prevalence of osteoporosis in community-dwelling postmenopausal women in China;
2. To identify risk factors for prevalent vertebral fractures in community-dwelling postmenopausal women in China;
3. To identify risk factors for densitometric osteoporosis in community-dwelling postmenopausal women in China.

2.3 Exploratory Objective(s)

1. To assess the diagnostic accuracy of onsite radiology imaging for vertebral fractures in China's local clinical practice;
2. To assess the diagnostic role of vertebral imaging for the screening of osteoporosis and pharmacological treatment in China's local clinical practice.

3 METHODOLOGY

3.1 Summary of Study Design

This study will be designed as an observational, population-based, cross-sectional study. A total of 2700 postmenopausal women over age of 50 inclusive and physically living in a community will be included in the study. As suggested by Chinese local guideline, postmenopausal women are eligible for a subsidized screening program (blood chemistry, radiology and/or DXA assessment) for osteoporosis clinical management. A cluster sampling (two-stage random sampling) by age and geographic region will be performed to represent a geographically generalized Chinese population with specific gender and age groups relevant to postmenopausal osteoporosis and VF prevalence. Subject recruitment will be based on various local demographic records including Government resident lists, local population lists, electoral registers, and health registers by a study invitation and a referral to the investigators at each study center. By 1 onsite visit, an interview, DXA measurement, and thoracic/lumbar spine X-ray will be performed to collect a set of data regarding socioeconomic/medical (interview-based questionnaire), VF assessment (radiographs), and specific densitometric information (BMD DXA) from the participant. No follow-up visit is required for this cross-sectional study unless a spine imaging and/or BMD measurement cannot be made during the visit due to a particular reason in the study or from the subject. The recruitment period is estimated between 6 and 9 months and initiated at any time point during a calendar year, because a seasonal or social impact on the data of interest is minimal. Analyses will be based on epidemiological data and then be expanded to establish a vertebral fracture risk assessment model.

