3.2 Study Population

This study will include approximately 2700 community-dwelling postmenopausal women aged 50 or above at 8 - 10 participating sites throughout China. A two-stage cluster sampling will be performed for the study. Firstly, geographic regions are divided into 'clusters' and then a randomized stratified sampling will be performed by age group using a computerized random selection on various demographic records (as indicated in Section 3.1) from the participating sites and the communities by which they cover. All subjects are expected to have an interview for questionnaire, vertebral imaging and BMD measurement. To be eligible for the study, participants must fulfill the following inclusion and exclusion criteria (Section 3.3 and 3.4):

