3.5 Stratification

The subjects will be sampled and stratified according to the following factors:

- 1) Age;

Seven (7) age groups: 50 - 54, 55 - 59, 60 - 64, 65 - 69, 70 - 74, 75 - 79, 80 or above;

- 2) Geographic region;

Five (5) regions in China: North, South, Southeast, Southwest, and Central

4 Variables and Epidemiological Measurements

All eligible participants will be included in the study to an endocrinologist, or other specialist, whenever appropriate, for the collection of all clinical and radiological information by 1 onsite study visit in a cross-sectional fashion. Spine radiograph and/or DXA may be separated from onsite interview by a follow-up visit as determined by the investigator.

Questionnaire

All demographic data, socioeconomic status, lifestyle information, and clinical features including medical history/concomitant medications, will be collected by an interviewer-administered questionnaire performed by the investigator. The questionnaire will be designed to adapt China's cultural and clinical practice. The analyzable variables derived from the questionnaire include (but not limited to):

- Age (absolute value and category);
- Place of birth and dwelling geographic region;
- BMI (height and weight, as measured in the site);
- Social status and lifestyle (educational level, occupation, monthly income, physical exercise, diet, smoking, alcohol intake, diet, calcium intake);
- Clinical features (age and years of menopause, medical history, history of osteoporosis and parental osteoporosis, any prior fractures, prior and concomitant medication, antiresorptive treatment, glucocorticoid treatment, other treatment reducing bone mass);
- FRAX score (as determined by self-reported fracture and radiology evidence and calculated based on the information from questionnaire with/without BMD).

BMD Measurement

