6.1.1 Administrative Procedures

6.1.1.1 Randomization and Study Invitation

In the study, 5 geographic regions will be identified as 'clusters' at the first stage. Within a region, a computer-generated randomization list by stratum (age) will then be produced separately in each participating site to identify and select specific invitees. All possible resources securing the participant's bio-information and contact details will be utilized to generate a full list of potential invitees. These resources include, but not limited to, Government resident lists, community-dwelling records, city council records, primary care health records and/or local health insurance records. Based on the sequence of the list, a numbered letter will be sent out to all women who are 50 years of age (inclusive) or above from the investigator to enquiry of their wish to attend the study. The letter to the women selected will explain the nature, the objectives and the study elements of the study. The receipt and acceptance of invitation will direct to the investigators by telephone, email, return of letter, or showcase the letter at the time of onsite screening. An advance notification by telephone or email may be practiced by the site investigator and/or study authorized staff to increase the rate of invitation acceptance.

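### The sampling is described as two-stage random and nationally representative, but only the draw of women within non-randomly chosen urban sites is random, and the pooled lists have no de-duplication rule

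*Combined protocol and SAP*

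**What the plan says.** Protocol section 3.1 gives the intended property: "A cluster sampling (two-stage random sampling) by age and geographic region will be performed to represent a geographically generalized Chinese population". Sections 3.2 and 8.2.1 repeat the two-stage cluster description, and 8.2.1 cites it among the measures against bias.

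The procedure is in section 6.1.1.1. For stage one, "5 geographic regions will be identified as 'clusters' at the first stage". Section 3.5 lists the same regions as a stratification factor: "Five (5) regions in China: North, South, Southeast, Southwest, and Central". Section 3.2 places the study "at 8 - 10 participating sites throughout China" and does not say how the sites are chosen. For stage two, "a computer-generated randomization list by stratum (age) will then be produced separately in each participating site".

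Section 3.1 names the list sources as "Government resident lists, local population lists, electoral registers, and health registers", section 6.1.1.1 adds "primary care health records and/or local health insurance records", and section 3.2 says the records come "from the participating sites and the communities by which they cover". Section 6.1.1.1 intends all sources to be combined into one complete list of possible invitees. Section 3.3 admits only women who have lived in an urban community for more than six months. Section 8.1.1 standardises overall and regional rates to the national age distribution of the 2010 census, with exact binomial and Wilson intervals.

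**The concern.** Prevalence is the primary objective, so the value of the result depends on who could have been selected and with what probability. Section 1.2 justifies the study partly because an earlier Beijing study represented only one city, and it calls for a nationwide, population-based investigation. If the sites are simply those taking part, the result describes their catchments. A site that is untypical of its region shifts that region's rate however many women it enrols. With 8 to 10 sites over five regions there are on average 1.6 to 2 sites per region, so regional and site differences are hard to separate.

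The lists raise a second question. A woman who appears on a resident list, a primary care record and an insurance record may be entered more than once, and a woman with no health record only once. If having a record is related to fracture within an age group, unequal chances of selection move the estimate. Age standardisation does not remove that part. The limitations in 8.2.3 cover low response, dropout and random error, but neither site selection nor list coverage.

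**Working it through.** **The plan's own figures.** The age-group sizes in Table 8.3.1 sum to 518. Allowing for 5% withdrawal, 518 / 0.95 = 545 per region, as stated in 8.3. Five regions give 5 × 545 = 2725, stated as about 2700. With 40% nonresponse and 5% ineligibility, 2700 / (0.60 × 0.95) = 4737 letters, stated as about 4750. These figures reproduce, but none bears on how sites or lists are chosen. The main point rests on the text.

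**Stated design against described procedure.**

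| Level | Label in the plan | What is described | Random? |
|---|---|---|---|
| Region | First-stage cluster (3.2, 6.1.1.1) | All five named regions used; also strata (3.5) | No draw described |
| Site | None | 8 to 10 participating sites (3.2) | No selection method given |
| Woman | Second stage | Computer-generated list by age stratum within each site (6.1.1.1) | Yes |

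A first stage that takes every unit is stratification. The level at which sampling could have generalised beyond the chosen places is the site, and no random step is described there. With the urban criterion in 3.3, the population reached by random sampling is urban postmenopausal women aged 50 or over in the catchments of the chosen sites.

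**List multiplicity.** Sections 3.1, 3.2 and 6.1.1.1 name population lists and care-based lists and say that they are to be combined. None names a base list, sets a coverage standard or requires repeat entries to be removed.

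**Illustration of size.** Input from the plan: the expected cases in Table 8.3.1 are 2.20 + 5.67 + 12.00 + 14.40 + 16.00 + 16.10 + 19.61 = 85.98, so mean prevalence is 85.98 / 518 = 16.6%. Assumed, with no support in the documents:

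- the share s of women on a health record is 40% to 80%;
- the odds ratio (OR) of fracture, on against off record within age group, is 0.8 to 2.0;
- every on-record woman is entered exactly twice and every other woman once.

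The two prevalences solve s × p_on + (1 - s) × p_off = 0.166 with odds(p_on) = OR × odds(p_off). Double entry raises the on-record share to w = 2s / (1 + s). The bias is (w - s) × (p_on - p_off).

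- s = 0.40, OR = 2.0: p_on = 0.2249, p_off = 0.1267, w = 0.5714. Bias = 0.1714 × 0.0982 = +1.7 points.
- s = 0.40, OR = 0.8: p_on = 0.1478, p_off = 0.1781. Bias = 0.1714 × (-0.0303) = -0.5 points.

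| OR | s = 40% | s = 60% | s = 80% |
|---|---|---|---|
| 0.8 | -0.5 | -0.5 | -0.3 |
| 1.0 | 0.0 | 0.0 | 0.0 |
| 1.2 | +0.4 | +0.4 | +0.2 |
| 1.5 | +1.0 | +0.8 | +0.5 |
| 2.0 | +1.7 | +1.3 | +0.7 |

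For comparison, the planned 95% half-width overall, with 2700 × 0.95 = 2565 readable radiographs, is 1.96 × sqrt(0.166 × 0.834 / 2565) = 1.4 points. Per region, with 518, it is 3.2 points. Both treat the women as a simple random sample.

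**The case against.** The strongest objection is to the inference that prevalence is biased toward women in care. The documents do not support that as a statement of fact. Government resident lists come first among the sources in 3.1 and 6.1.1.1, and all sources are to be combined into one complete list. If the resident list is complete, every woman has at least one chance, and the remaining defect is possible duplicates. A reader might also work out the bias at a site that draws only from health records: the same assumptions with an OR of 1.2 to 2.0 give +0.5 to +5.9 points. No section plans such a frame, so that range should not be used.

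Three further objections have force. First, the sign in the illustration comes entirely from the assumed OR, and an OR below 1 reverses it. At 90% to 95% coverage and an OR of 1.5, the bias is only 0.1 to 0.2 points. Second, women are drawn within age strata and the overall and regional rates are age-standardised, so any link between health records and fracture that runs through age is largely removed. Third, the records mentioned in 3.2 are demographic records, which need not mean patient files, and 8.2.1 claims only that the sampling may limit volunteer effect. Random invitation of listed women can help with that even if the sites are not random.

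None of this supplies a random selection of sites, turns an urban sample into a national one, or provides a de-duplication rule.

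**Conclusion.** The described procedure does not have the stated design property. Region and age are strata, no random selection of sites is described, eligibility is urban, and only the draw of women within a site is random. The design therefore does not support a claim to represent a geographically generalised Chinese population. This conclusion rests on the text alone and needs no assumption.

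The missing de-duplication rule is a second, smaller defect. It can give women unequal chances of selection, so coverage bias is possible, but its size and sign cannot be derived from the documents. If every on-record woman were entered twice, the illustrative range is about -0.5 to +1.7 points around 16.6%. The upper end slightly exceeds the overall half-width of about 1.4 points, and the whole range lies inside the regional half-width of about 3.2 points. The coverage, odds ratio and double entry behind it are all assumed.

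The plan should be changed on both counts. The list rule has to be set before invitations go out, because unrecorded selection chances cannot be recovered at analysis.

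**What to change.** 1. In 3.1, 3.2, 6.1.1.1 and 8.2.1, describe the design as it is: region and age are strata, sites are not randomly selected (or, if they were, say how), and women are randomly sampled within site catchments. State the prevalence conclusion for urban women in those catchments. Add site selection and list coverage to the limitations in 8.2.3.
2. In 6.1.1.1, require each site to merge its lists and remove duplicates before randomisation, so that each woman has one entry, and to record the source list or lists for every invitee. A de-duplicated union is preferable to a resident-list-only rule, which could lose eligible women who appear only on other lists.
3. In 8.1.1 and Table 8.1.1.1, add age-standardised prevalence by site, so that an untypical site can be seen within its region.

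The cost is protocol wording, some list-preparation work at each site, one extra table and a more modest claim of national representation. No additional participants or visits are needed.
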